1. BACKGROUND AND SIGNIFICANCE

Radical cystectomy is the gold standard treatment for muscle-invasive bladder cancer. It involves removal of the bladder and prostate for men and anterior exenteration (including the bladder, uterus, ovaries, and part of the vagina) for women. Patients who were treated with the surgical approach report poor overall satisfaction, sexual function, urinary and bowel function, and health-related quality of life. The current NCCN (National Comprehensive Cancer Network) Clinical Practice Guidelines (version 2.2015) indicates bladder-preserving therapy with cystectomy reserved for tumor recurrence represents a safe and effective alternative to immediate radical cystectomy for muscle invasive bladder cancer.

According to the current NCCN guidelines, patients who are not surgical candidates (i.e. those with extensive comorbidities and/or poor performance status), chemoradiation can be used as a curative treatment regimen. This bladder-sparing therapy consist of (1) maximal transurethral resection of bladder tumor (TURBT), (2) induction external-beam radiation therapy with concurrent chemotherapy, (3) cystoscopic assessment of treatment response with prompt cystectomy for non-responders, and (4) active cystoscopic surveillance with salvage cystectomy at the first sign of invasive recurrence.

Retrospective studies have shown that the majority of chemoradiation patients achieves a clinical response and preserves the native bladder in >70% of patients while offering long-term survival rates comparable to contemporary cystectomy series.^{1,2}

We hypothesize that chemoradiation is non-inferior to radical cystectomy with regard to quality of life and progression free and bladder intact survival. Short of a randomized trial, any direct comparison of chemoradiation to radical cystectomy to address our hypothesis is difficult and must account for selection bias and confounding variables resulting from discordance between clinical, pathologic staging, functional status and comorbidities. Our proposed randomized pilot non-inferiority study aims to provide feasibility data for a larger randomized clinical non-inferiority trial comparing the efficacy and safety of chemoradiation and radical cystectomy.

Given the potential non-inferiority of chemoradiation relative to radical cystectomy, clinical prediction of non-response to chemoradiation in terms of biomarkers would be of interest. However, there is paucity of predictive markers that can identify non-responders of chemoradiation. If predictive markers could be identified, patients might then be selected for the treatment most likely to benefit them, which would have the added advantage of maximizing overall cure rates and minimizing poor outcomes. Characterization of the genomic drivers of bladder cancer has been proposed for evaluating progression. Immunohistochemistry has been utilized with limited accuracy. A number of investigators have queried whether comprehensive genomic profiling of cancer-related genes could potentially assist in the selection of targeted therapies for patients with radiation refractory bladder cancer.³ As part of our pilot study, we propose to perform microarray gene expression profiling using Agilent long oligonucleotide (60 mers) technology to search for molecular alterations differing between responders and non-responders of chemoradiation with radical cystectomy as a reference.

1.1. PRELIMINARY DATA

1.1.1. **Data on Chemoradiation:** The Kaplan–Meier plot in Figure 1 (copied from Reference 1) shows 348 patients with muscle invasive bladder cancer who underwent chemoradiation at Massachusetts General Hospital (MGH) by response (incomplete, complete). For clinical stage T2, three-year disease specific survival rates were 74% and 50% for patients who were complete and incomplete responders respectively.¹ The MGH Kaplan Meier curves for disease-specific survival suggest that response to chemoradiation may contribute to the non-inferiority of chemoradiation relative to radical cystectomy with regard to progression free survival in this study [Section 2, Specific Aim 1b].

[figure not shown]

Figure 1: Kaplan Meier plots for disease-specific survival following chemoradiation for all stratified by induction response status in the MGH study¹.

1.1.2. **Role of genome sequencing:** In a radiotherapy test cohort ($n = 201$), high tumor MRE11 expression (one of the candidate genes in our research) in patients receiving radiotherapy (RT) was associated with better cancer-specific survival compared with cystectomy [70% versus 55% 3-year cause-specific survival (CSS), $P = 0.021$]⁴, suggesting that MRE11 expression may play an important role with regard to predicting response to chemoradiation [Section 2, Specific Aim 2a]. Figure 2 shows the relevant plots copied from Reference 4.

[figure not shown]

Figure 2: Kaplan-Meier CSS curves for low and high MRE11 Radiation Therapy (RT) compared to cystectomy

2. HYPOTHESIS AND SPECIFIC AIMS

Multiple prospective radiation therapy protocols have evaluated bladder-preserving chemoradiation therapy approach for muscle-invasive bladder cancer (MIBC), with radical cystectomy reserved for radiation failure. Aims of bladder preservation in MIBC are to offer a quality-of-life advantage and avoid potential morbidity or mortality of RC without compromising oncologic outcomes. Because of lack of level-1 evidence, oncologic equivalence of bladder preservation modality treatments compared with RC remains unknown.

2.1 HYPOTHESIS:

We hypothesized that chemoradiation is non-inferior to radical cystectomy for treatment of MIBC.

2.2 SPECIFIC AIMS:

SPECIFIC AIM 1a To determine and quantify quality of life in patients treated with radical cystectomy and chemo radiation therapy

1b To determine and quantify progression free survival and bladder-intact survival in patients treated with radical cystectomy and chemoradiation therapy,

SPECIFIC AIM 2a To evaluate genetic markers predicting response to chemoradiation by performing tissue RNA microarrays.

2b To assess the feasibility of conducting an adequately powered non-inferiority trial of the same design via recruitment rate, patient adherence to both treatment arm, and attrition.

2.3 STUDY DESIGN:

Our study will be a pilot, prospective, single-center, randomized non-inferiority trial comparing chemoradiation therapy to radical cystectomy. Patients diagnosed with muscle invasive bladder cancer after transurethral resection of bladder tumor and are surgical candidates will be randomized to either radical cystectomy (with neoadjuvant chemotherapy if suitable candidate) or chemoradiation.

Both treatment methods are considered “standard of care” recommended by the NCCN Clinical Practice Guidelines (http://www.nccn.org/professionals/physician_gls/pdf/bladder.pdf) in treating muscle invasive bladder cancer.

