Categorical outcomes will be summarized with frequencies and percentages. Continuously distributed outcomes will be summarized with the sample size, mean, standard deviation, median, minimum and maximum. A consort diagram giving the number patients screened, the number of screen failures, the number randomized, the number lost to follow-up by reason, and the number completing the study by treatment arm will be created. In Aim 1a we will test the hypothesis that chemoradiation therapy is non-inferior to radical cystectomy with regard to change in quality of life at 36 months relative to baseline. In Aim 1b, we will test the hypothesis that chemoradiation is non-inferior to radical cystectomy with regard progression free survival and bladder intact survival. With regard to Aim 1a, assuming the 50% (p_2) of patients randomized to radical cystectomy and 60% (p_1) of patients randomized to chemoradiation will experience improvement in quality of life at 3 years relative to baseline and a 5% margin (Δ) of non-inferiority, this study would require $n=171$ subjects per group to attain 80% power for testing $H_0: p_1 - p_2 \leq \Delta$ versus $H_1: p_1 - p_2 > \Delta$ with $\alpha=5\%$. The non-inferiority of chemoradiation compared with radical cystectomy with regard to changes in quality of life (Aim 1a) will be assessed with Fisher's exact test. Progression free and bladder-intact survival (Aim 1b) will be summarized by treatment arm with Kaplan-Meier curves and supporting tabulations and non-inferiority will be assessed with a logrank test. The significance of treatment arm differences with regard to biomarkers (Aim 2a) will be assessed with t-tests or Wilcoxon tests. Pairwise correlations between biomarkers will be displayed overall and by treatment arm. Logistic regression will be used to find a best linear predictor of treatment arm in terms of multiple biomarkers. Biomarkers may be log transformed prior to analysis. Feasibility (Aim 2b) will be assessed with a new power and sample size calculation. If the logistic regression model fails in Aim 2a, random forests will be attempted. If the logrank test fails in Aim 1b, Fisher's exact test will be used. R (v3+, Vienna, Austria) or SAS (SAS Institute, Cary, North Carolina) software will be used throughout.

REFERENCES

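### Section 11 states a 5-point quality-of-life non-inferiority margin but names a test that cannot use it, and gives no rule for concluding either non-inferiority or an advantage

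*Combined protocol and SAP*

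**What the plan says.** Section 2 opens with the general case for the treatment strategy: "Aims of bladder preservation in MIBC are to offer a quality-of-life advantage and avoid potential morbidity or mortality of RC without compromising oncologic outcomes". The trial's own hypothesis follows in Section 2.1: "We hypothesized that chemoradiation is non-inferior to radical cystectomy for treatment of MIBC". Section 1 applies it to QoL by name: "We hypothesize that chemoradiation is non-inferior to radical cystectomy with regard to quality of life and progression free and bladder intact survival". Aim 1a in Section 2.2 is descriptive: "To determine and quantify quality of life in patients treated with radical cystectomy and chemo radiation therapy".

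Section 11 turns Aim 1a into a test: "we will test the hypothesis that chemoradiation therapy is non-inferior to radical cystectomy with regard to change in quality of life at 36 months". Its planning assumption is a benefit: "assuming the 50% (p_2) of patients randomized to radical cystectomy and 60% (p_1) of patients randomized to chemoradiation will experience improvement in quality of life". With a 5% margin and alpha of 5% (sidedness not given), "this study would require $n=171$ subjects per group to attain 80% power". The null is written as p1 - p2 at or below Δ, with no minus sign. Fisher's exact test is the named analysis. Section 11 specifies no superiority reading of QoL and no order of conclusions.

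The study itself randomizes 30 patients, 15 per arm. For Aim 2b, Section 11 says feasibility will be judged by a fresh power and sample size calculation.

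**The concern.** Two things do not fit together.

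First, the margin enters the sample size but not the analysis. Fisher's exact test asks whether the two improvement rates are equal. A significant result favouring chemoradiation would be evidence against equality. A non-significant result would not show that chemoradiation is at most 5 points worse. The plan does not say which Fisher result would count as non-inferiority, so the stated hypothesis has no decision rule.

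Second, the rationale for bladder preservation is better QoL, and the planning rates assume it, yet nothing prespecifies how an advantage would be concluded. If the data pointed that way, the claim would look post hoc.

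The larger trial has most at stake. Aim 2b concerns an adequately powered trial of the same design, and Section 11 offers one worked calculation as a pattern. Its 80% refers to non-inferiority only and says nothing about the chance of showing the benefit that the same calculation assumes.

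**Working it through.** **Inputs, all from Section 11:** p1 = 0.60 (chemoradiation), p2 = 0.50 (cystectomy), margin 0.05, power 80%, alpha 5%, stated size 171 per group. Actual size: 15 per arm. Variance term: 0.60 × 0.40 + 0.50 × 0.50 = 0.24 + 0.25 = 0.49.

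**1. Reproduce 171.** Take the null as p1 - p2 ≤ -0.05, so the distance from the null is 0.10 + 0.05 = 0.15.
- One-sided 2.5% (two-sided 5%): n = (1.96 + 0.8416)² × 0.49 / 0.15² = 7.849 × 0.49 / 0.0225 = 170.9, so 171. This matches.
- One-sided 5%: n = (1.645 + 0.8416)² × 0.49 / 0.0225 = 134.6, so 135. This does not match.
- Null as printed, with Δ = +0.05: the distance is 0.10 - 0.05 = 0.05 and n = 7.849 × 0.49 / 0.0025, which gives 1,539 per group at one-sided 2.5%. This does not match.

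So 171 implies a null of minus 5 points at one-sided 2.5%. The missing minus sign is a slip in the text, not in the calculation.

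**2. What the named test delivers at 171 per group.** Exact enumeration of Fisher's test at 60% v 50% gives rejection in 41.5% of trials at two-sided 5%. The 80% belongs to a comparison with minus 5 points, which Fisher's test does not make.

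**3. Power to show an advantage at 171 per group, two-sided 5%.** Pooled rate 0.55, so 2 × 0.55 × 0.45 = 0.495.
- z = (0.10 - 1.96 × sqrt(0.495/171)) / sqrt(0.49/171) = (0.10 - 0.1055) / 0.0535 = -0.10, so power is 45.9%.
- With the unpooled standard error, as in a simple confidence interval: z = 0.10/0.0535 - 1.96 = -0.09, so power is 46.3%.

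**4. Size for 80% power to show an advantage, two-sided 5%.** n = (1.96 × sqrt(0.495) + 0.8416 × sqrt(0.49))² / 0.10² = (1.379 + 0.589)² / 0.01 = 387.3, so 388 per group before dropout. In total, 2 × 388 = 776 patients against 2 × 171 = 342.

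**5. Sensitivity to sidedness.** If alpha were one-sided 5%, power for an advantage at 171 would be 58.5% (Fisher 53.2%) and 305 per group would give 80%. That reading does not produce 171.

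**6. The pilot, 15 per arm.**
- Non-inferiority, one-sided 2.5%: z = 0.15 / sqrt(0.49/15) - 1.96 = 0.830 - 1.96 = -1.13, so power is about 13%.
- Advantage, two-sided 5%: z = (0.10 - 1.96 × sqrt(0.495/15)) / sqrt(0.49/15) = -0.256 / 0.181 = -1.42, so power is about 8% (Fisher 3.3%).

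**The case against.** The strongest reply is that nothing promised goes untested. The Section 2 sentence on a QoL advantage describes bladder preservation in general; the passage goes on to name oncologic equivalence as the unknown. The trial's hypothesis is non-inferiority in Sections 1, 2 and 11, and Aim 1a only sets out to measure QoL. Every non-inferiority design has less power against zero than against its margin. Section 11 also commits Aim 2b to a new size calculation, and it never labels 171 as the size of the later trial. With 15 per arm, a second reading after a first that is met about one time in eight changes little here.

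Most of this stands, and it rules out three stronger readings that a reader might infer:
- That the analysis contradicts the trial's objective. It does not: the objective is non-inferiority, and the advantage is background rationale.
- That the plan could never conclude a QoL advantage. Fisher's exact test is a test against zero, and an interval lying wholly above 0 would show one. What is missing is prespecification.
- That the larger trial will be run at 171 per group. The documents promise a recalculation.

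The reply does not cover the mismatch between margin and test. A non-inferiority hypothesis with a stated margin needs an analysis that uses that margin, whatever the sample size.

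**Conclusion.** The point holds as a gap in the analysis rule. Section 11 sizes Aim 1a on a 5-point margin, names a test without one, and gives no criterion for concluding either non-inferiority or the advantage it assumes. At the plan's own rates and 171 per group, the intended non-inferiority comparison has 80% power, the named test rejects about 42% of the time, and an advantage would be shown about 46% of the time.

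These figures rest on the 60% and 50% rates, on two-sided 5% (one-sided 2.5%), which is the reading that reproduces 171, and on no dropout. In the pilot, power is about 13% for non-inferiority and 8% for an advantage, so the change will seldom alter this study's conclusion. Its value lies in a correct rule and in what the Aim 2b calculation hands to the larger trial.

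**What to change.** In Section 11, for Aim 1a:
- Replace Fisher's exact test with one two-sided 95% confidence interval for p1 - p2 (chemoradiation minus cystectomy), and name the interval method.
- Write the null as p1 - p2 ≤ -5 percentage points.
- Read the interval in fixed order. Non-inferiority is concluded if the lower limit is above -5 points; only then is an advantage concluded if the lower limit is also above 0. The fixed order needs no alpha adjustment.
- Beside 171, state that the 80% is for non-inferiority at two-sided 5% (one-sided 2.5%), that power to show an advantage at the assumed rates is about 46%, and that 80% would need about 388 per group before dropout. Ask the Aim 2b calculation to report both.

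If the investigators want only non-inferiority on QoL, they should say so and why; the interval and the corrected null are still needed.

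The cost is a few sentences, with no extra patients, data or alpha. The named test has to be removed, not supplemented, or Section 11 would hold two conflicting analyses of Aim 1a. A less favourable power figure will stand next to the 80%.

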3. STUDY ENROLLMENT AND WITHDRAWAL

3.1 Inclusion Criteria:

3.1.1 Pathologically (histologically) proven diagnosis of primary carcinoma of the bladder (transitional cell cancer) within 8 weeks of registration. Operable patients whose tumors are primary carcinomas of the bladder and exhibit histologic evidence of muscularis propria invasion and are AJCC clinical stages T2-T4a, Nx or N0, M0

3.1.2 Patients without histologically or cytologically confirmed node metastases or any other metastases

3.1.3 Patients must have an adequately functioning bladder after thorough evaluation by an urologist and have undergone as thorough a transurethral resection of the bladder tumor as is judged safely possible.

3.1.4 Patients must be considered able to tolerate systemic chemotherapy combined with pelvic radiation therapy, and radical cystectomy.

3.1.5 History and physical examination including weight, performance status, and body surface area within 8 weeks prior to study registration

3.1.6 Zubrod (ECOG) Performance Status 0-2

3.1.7 Age \geq 18;

3.1.8 CBC/differential obtained no more than 4 weeks prior to registration on study, with adequate bone marrow function defined as follows:

- a) WBC \geq 4000/ml
- b) Absolute neutrophil count (ANC) \geq 1,800 cells/mm³;
- c) Platelets \geq 100,000 cells/mm³;
- d) Hemoglobin \geq 10.0 mg/dl (Note: The use of transfusion or other intervention to achieve Hgb \geq 10.0 g/dl is acceptable.);

3.1.9 Patient's comprehensive metabolic panel (CMP) must be done no more than 6 weeks prior to informed consent and the CMP levels must be within acceptable institutional limits or to the discretion of the treating physician, which may be the principal investigator of the study.

3.1.10 Serum pregnancy test for female patients of childbearing potential, \leq 72 hours prior to study entry; women of childbearing potential and male participants must practice adequate contraception.

3.1.11 Patient must be able to provide study-specific informed consent prior to study entry

3.2 Exclusion Criteria:

3.2.1 Unable and unwilling to provide informed consent

3.2.2 Evidence of distant metastases or histologically or cytologically proven lymph node metastases

3.2.3 Previous systemic chemotherapy (for any cancer) or pelvic radiation therapy

3.2.4 A prior or concurrent malignancy of any other site or histology unless the patient has been disease-free for \geq 5 years except for non-melanoma skin cancer and/or stage T1a prostate cancer or carcinoma *in situ* of the uterine cervix

3.2.5 Patients judged not to be candidates for radical cystectomy; patients with pN+ or T4b disease are considered to have unresectable disease

3.2.6 Severe, active co-morbidity, defined as follows:

- Unstable angina and/or congestive heart failure requiring hospitalization within the last 6 months;
- Transmural myocardial infarction within the last 6 months;

- Acute bacterial or fungal infection requiring intravenous antibiotics at the time of registration;
- Chronic Obstructive Pulmonary Disease exacerbation or other respiratory illness requiring hospitalization or precluding study therapy at the time of registration;
- Hepatic insufficiency resulting in clinical jaundice and/or coagulation defects; note, however, that laboratory tests for liver function and coagulation parameters are not required for entry into this protocol.
- Acquired Immune Deficiency Syndrome (AIDS) based upon current CDC definition; note, however, that HIV testing is not required for entry into this protocol. The need to exclude patients with AIDS from this protocol is necessary because the treatments involved in this protocol may be significantly immunosuppressive. Protocol-specific requirements may also exclude immuno-compromised patients.

3.2.7 Pregnancy or women of childbearing potential and men who are sexually active and not willing/able to use medically acceptable forms of contraception; this exclusion is necessary because the treatment involved in this study may be significantly teratogenic.

3.2.8 Is pregnant; women of childbearing potential and male participants unwilling to practice adequate contraception.

3.3 Randomization Procedure

A total of 30 patients will be randomized to either chemoradiation group (n=15) or radical cystectomy (with or without neoadjuvant chemotherapy group, n=15). Permuted block randomization process through sequentially numbered, opaque sealed envelopes will be utilized in assigning participants into either radical cystectomy or chemoradiation group. All subjects will be randomized in blocks of size 2. A randomization list containing sequence numbers and treatment assignments will be prepared by the statistician and used as the sole basis for treatment assignments throughout the study.

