4. SCHEDULE OF EVENTS

This study requires a minimum of nine study visits to the MARC, CTRC, and/or UHS. The research staff will try to schedule these study visits at the same time as the patient's routine follow-up visits as much as possible to lessen the participant's burden. Since this study is a comparison of two standard of care treatments, participant will not be limited to receiving treatments (i.e. radical cystectomy, radiation, and/or chemotherapy) at UTHSCSA affiliated medical facilities. If participant choose to receive treatment (i.e. radical cystectomy, radiation, and/or chemotherapy) outside of UTHSCA affiliated medical facilities and still would like to remain in the study, we will request for the participant to release his/her medical records and treatment summaries from outside facilities to us after treatment completion. Participant will return to MARC, CTRC, and/or UHS for the routine post-treatment follow-up visits with the treating Urologist. The specific location for the follow-up routine visits will be to the discretion of the treating physician and also the participant's insurance coverage. A summary of study schedule of events is as follows:

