4.1 Screening and enrollment

Research staff will review clinic schedules to identify potential participants. Treating Physicians/Physician's Assistant/Nurse Practitioner seeing patients at the MARC Urology Clinics, CTRC will also identify study candidates. Advertising material such as a study flyer will also be placed in the Urology clinics to facilitate with participant recruitment. Potential study candidates identified by the research staff and the information regarding study eligibility will be made available to the treating physician who provides clinical care and sees the patient in clinic. The treating physician, physician assistants (PA), or nurse practitioner (NP) will make initial contact with patients whose pre-screening/chart review indicates they may be eligible for study participation.

Interested participants may also contact the research staff, and if determined possibly eligible for study participation, are scheduled for a research appointment. Screening information collected on ineligible participants will be shredded at the end of study recruitment.

Once the patient has been determined to meet pre-screening criteria, potential participants will first be approached in their private examination room by their treating medical provider, who may also be a research investigator. If the patient indicates an interest in study participation, he will be provided further information about the study, answer questions, and provide a copy of the consent form. The individual will be encouraged to take the consent form home to read and discuss with family, friends, or physicians. If interested, the potential participant will be scheduled to come in and sign consent and undergo study assessments.

The technical aspects of the study will be discussed with potential participants by the Principal Investigator, approved research team members and/or by study co-investigators. Research staff members who are IRB approved and designated for that role will conduct the consent process. The following consent elements will be discussed: voluntary nature of participation, purpose of the study, study procedures, risks and benefits, the collection of protected health information, confidentiality, and participant rights. The participant will be given a copy of the informed consent

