to read and consider and ample opportunity will be given to answer any questions. The participant may decline to participate, decide to participate, or take the consent home to think about participating. A copy of the signed consent form will be provided to each participant.

The potential participant will then be scheduled for a TURBT (transurethral resection of bladder tumor) with the treating urologist, which may also be the study's principal investigator or co-investigator. TURBT is the standard of care which allows the treating urologist to formally assess the extent of disease progression and also to evaluate whether the candidate can be treated with both radical cystectomy and chemoradiation treatment. Potential participant will be approached to store any leftover tissue specimens, not needed for diagnosis, into the "GU Tissue Bank" (IRB HSC20050234H). The tissue collected will be processed per standard of care, and slides or tissue blocks may be accessed later for future use in correlative studies. The leftover specimens may be used for future research studies that may include genetic testing related to bladder cancer. This banking portion is optional and not required to be in the main study. If the participant declines to participate in the optional study, any leftover specimens will be permanently de-identified through the GUTB (05-234H).

The potential participant will then return to the clinic for a routine follow-up visit to review the TURBT results and discuss treatment options with the treating Urologist within 4 weeks post-TURBT. Final eligibility will be determined during the TURBT follow-up visit. If potential participant is eligible for the study, randomization will occur. The following section outlines study procedure during the visit.

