4.2 Baseline Visit

The potential participant will return to the urology clinic to review pathology results and treatment options within 4 weeks of TURBT. This is a routine post-TURBT follow-up visit (i.e. baseline visit). If the potential participant is deemed eligible for both radical cystectomy and chemoradiation by the treating urologist, the potential participant will then be randomized either to radical cystectomy arm or chemoradiation arm.

Each participant will be assigned a unique subject identifier (subject ID) that has no meaning external to the study database. The participant identifiers will be further masked and password protected, and stored only on a secure server behind a "firewall". Only authorized research study members will have access to these identifiers. A research study file will be kept for each participant accrued. This file will include the participant's consent, the assigned unique subject identifier, and copies of relevant source documents. All participant records will be securely stored in the Urology research offices at the MARC. A data entry system will be prepared in RedCap for the study. Both the subject identifier, sequence number, and the treatment assignment for each patient will be entered into the database together with clinical outcome data collected across visits.

During this visit, the participant will complete a study questionnaire packet, which may include and not limited to demographics, medical history; and study questionnaires *such as* EORTC QLQ C30 and FACT-BI. In the interest of time, the study questionnaire packet may also be completed at participant's home and return to the study team via mail or email (per participant preference). Study team member will strongly encourage participant to complete the study questionnaire at

the time of baseline visit. If the participant completes the questionnaires from home, a study team member may follow-up with the participant over the phone, if the completed questionnaires are not received within a week of the visit. Two tubes (~ 10 mL or 2 teaspoons each) of research blood will also be drawn. Study team member or clinic staff will record participant's height, weight, and vital signs. At the completion of the baseline measurements, each participant will be randomized to either "Radical Cystectomy" or "Chemoradiation" following a process through sequentially numbered, opaque sealed envelopes by an authorized research study member.

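### Every block is fixed at 2 and the size is printed in the protocol, so up to 15 of the 30 assignments can be deduced before the final eligibility decision.

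*Combined protocol and SAP*

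**What the plan says.** Section 3.3 randomises 30 patients 1:1, 15 per arm, by permuted blocks with sequentially numbered, opaque, sealed envelopes. The statistician prepares one list, which is the only basis for assignment. The block size is explicit: "All subjects will be randomized in blocks of size 2". No stratification factor is named. Section 2.3 describes the design: "Our study will be a pilot, prospective, single-center, randomized non-inferiority trial".

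On timing, Section 4.1 says: "Final eligibility will be determined during the TURBT follow-up visit". Section 4.2 makes randomisation conditional on the urologist's view: "If the potential participant is deemed eligible for both radical cystectomy and chemoradiation by the treating urologist". An authorised study member then uses the envelopes to make the assignment. Section 4.1 has the patient "approached in their private examination room by their treating medical provider, who may also be a research investigator".

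On who can see earlier assignments, Section 4.2 says: "Both the subject identifier, sequence number, and the treatment assignment for each patient will be entered into the database". It restricts access to participant identifiers, but it does not say whether those who decide eligibility can see the assignments.

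Part of the eligibility decision is judgement. Criterion 3.1.4 reads: "Patients must be considered able to tolerate systemic chemotherapy combined with pelvic radiation therapy, and radical cystectomy". Criterion 3.2.5 likewise excludes patients judged unsuitable for cystectomy.

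**The concern.** In a block of 2 the second assignment is always the opposite of the first. Opaque envelopes hide what is inside them, but they do not stop anyone working out the next assignment from the previous one. Two facts are needed: the last assignment, and its place in the pair. The first is easy to learn in a single-centre trial of surgery against chemoradiation. The second follows from whether the envelope number is odd or even, and the sequence number is also stored beside the assignment in the database.

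The eligibility decision comes before the envelope is opened, and it rests partly on judgement. A clinician who knows the next assignment could, without any intent to mislead, judge a borderline patient differently or change the order in which two patients are seen. Consent is obtained before TURBT, so selective consent is largely ruled out; the eligibility call and the order of visits are the main routes left.

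Section 1 gives selection bias as the reason a randomised comparison is needed. Deducible assignments can let that bias back in. The stakes are the credibility of the between-arm comparisons in Section 11 and, through Aim 2b, a larger trial that would copy this design.

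**Working it through.** **Inputs.** From Section 3.3: 30 patients, 1:1, fixed blocks of 2, one list, numbered envelopes. From Section 2.3: one centre. The number of recruiters, and what each can see, are not stated, so they are treated as assumptions.

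**The plan's own figure.** 30 / 2 = 15 complete pairs, each with one patient per arm, which gives 15 + 15. This reproduces the stated allocation.

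**Predictability with blocks of 2, previous assignment and pair position known.**
- Certain: one per pair, 15 × 1 = 15 of 30 (50%).
- Best guess: (15 × 0.5 + 15 × 1) / 30 = 22.5 / 30 = 75%. Simple randomisation would give 15 / 30 = 50%.

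**Partial knowledge.** Suppose *k* recruiters share patients equally at random, each seeing only their own assignments but knowing the pair position. The chance that one recruiter handles both patients of a pair is 1/*k*. Certain assignments are then 15/*k*, and the best-guess rate is 50% + 25%/*k*.

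| Recruiters | Certain of 30 | Best guess |
|---|---|---|
| 1 | 15 | 75% |
| 2 | 7.5 | 62.5% |
| 3 | 5 | 58.3% |

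**Randomly varying blocks of 4 and 6.** There are 28 orders of 4s and 6s that sum to 30. Lists were simulated, drawing the order uniformly, with an observer who knows the two sizes and all earlier assignments but not the order of the blocks.

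| Patients to randomise | Certain, blocks of 2 | Certain, 4/6 | Certain, 4/6, total also known |
|---|---|---|---|
| 30 | 15 | about 1.5 | about 3.0 |
| 20 | 10 | about 1.1 | about 2.6 |
| 10 | 5 | about 0.7 | about 1.9 |

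For 30 patients the best-guess rate is about 69–70%, or about 21 of 30. If the 4/6 list is simply cut off at 30, about 1.7–1.8 are certain.

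**What varying blocks cost in balance (lists of 30).**
- The largest running imbalance is 1 in about 2% of lists, 2 in about 75% and 3 in about 23%.
- If recruitment stops after *n* = 1 to 29 patients, all *n* equally likely, the remaining imbalance is 2 in 11.2% and 3 in 0.9%, so 2 or more in about 12%.
- Blocks of 2 never leave an imbalance above 1.

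**The case against.** The strongest reply is that foreknowledge by the person deciding eligibility is possible but not shown. An authorised study member handles the envelopes, and nothing says that this is the urologist or that the urologist sees the numbers. The point about the database rests on silence. Sections 4 and 4.1 describe several kinds of provider and several locations ("This study requires a minimum of nine study visits to the MARC, CTRC, and/or UHS"), which moves the figure towards 7.5 or 5. This stands, and it is why 15 is given as a ceiling. It does not remove the weakness, because no provision keeps earlier assignments from those who decide eligibility.

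Second, the route to bias is narrow. Patients consent before TURBT and must be fit for both treatments, and many criteria are objective. The Section 9.7 count of patients found ineligible after TURBT, with reasons, and the planned CONSORT diagram would help to expose selection. This is also fair, but such records can only detect selection; they cannot correct it.

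Third, this is a 30-patient pilot whose feasibility measures depend little on allocation, and blocks of 2 guarantee near balance at any stopping point. That limits the weight of the point. However, Section 11 still plans non-inferiority comparisons between arms.

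Fourth, varying the blocks lowers the best-guess rate by only 5 to 6 percentage points. That is correct. The gain lies in removing certainty. Finally, Section 3.4 allows withdrawal of a patient considered not to be a candidate for chemoradiation after an oncology consult. That is a separate issue, and a change of block size would not affect it.

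**Conclusion.** The concern holds. With fixed, disclosed blocks of 2, up to 15 of 30 assignments are certain in advance, provided the previous assignment and its place in the pair are known. Both are plausible here. If assignments are kept within two or three recruiters, the expected number is about 7.5 or 5. Section 11 aims for 30 evaluable patients; if more are randomised to reach that, the ceiling is half the larger number.

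These figures measure predictability, not bias. The documents do not show that selection took place and give no basis for its size or direction. For a feasibility pilot this is an avoidable weakness in allocation concealment that should be corrected because the correction is cheap. It is not a reason to dismiss the trial.

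**What to change.** For all patients not yet randomised, the statistician should prepare a new list with randomly varying block sizes, for example 4 and 6, summing to the number remaining and starting once any open pair is closed. The list and the block sizes should be kept from everyone who recruits or decides eligibility, and the block size should be removed from Section 3.3. Section 4.2 should also say that these people cannot see sequence numbers and assignments in the database.

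The cost is a new list and a short amendment; sample size, treatments, visits and analysis are unchanged. The 15:15 split is kept only if all 30 are randomised, and an early stop could leave the somewhat larger imbalance shown above. The documents do not say whether anyone has been randomised, although Section 9.7 shows that this version post-dates the IRB approval of April 15, 2016. A new list protects only later patients and cannot undo what staff already know, so the benefit shrinks as fewer remain.
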